Three hundred participants (identified as heavy smokers) will be recruited. All participants will complete an experimental cued threat task (No shock/Predictable shock/Unpredictable shock, or NPU, as described above) designed to assess the affective components (fear, anxiety) of their response to stressors in the laboratory to test for stress neuroadaptation resulting from chronic smoking. Participants will complete the task twice in two separate experimental sessions on separate days. The first time they will be either nicotine deprived and/or non-deprived (counterbalanced). Participants are randomly assigned to one of two treatments (Combo NRT with counseling or placebo NRT with counseling) and schedule a quit date. All participants will provide 3 weeks (1 week pre-quit; 2 weeks post-quit) of 4x daily, real-time report of stressors, affective state, urge to smoke, actual cigarette use, and study medication adherence. Participants return to the laboratory at 2 weeks post-quit. At this follow-up visit, stressor exposure, affective status, withdrawal symptoms, smoking urge, tobacco use, and medication adherence will be measured. Biological confirmation (CO measurement) of recent smoking is also obtained. At the 2 week post quit visit, they complete the second administration of the experimental cued threat task.

C2: GENERAL METHODS AND MEASURES

This section provides detail on the general methods and measures in this application. A separate section (C3) details the experimental cued threat task.

C2.1: Participants. Three hundred smokers (approximately 1/3 female as represented in the Madison smoking community) will be recruited. Inclusion criteria include cigarette use ≥ 10 cigarettes/day \geq two years, smoke within the first 30 minutes of waking up, expired air carbon monoxide (CO) level ≥ 6 ppm, self-reported motivation to quit smoking, ability to read and write English, and an agreement to respond to EMA prompts throughout the day for three weeks. Health screening will ensure that participants can safely use the nicotine patch and lozenge. Specifically, participants will be excluded for FDA contraindications for NRT (e.g., no uncontrolled hypertension, recent myocardial infarction, diabetes, heart disease, asthma, stomach ulcers). All women of child-bearing potential will be required to agree to use an approved method of birth control to prevent pregnancy during the course of the study.

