On arrival at the laboratory for each of both experimental sessions, participants report the time of their last cigarette and have their CO level measured. For the nicotine deprived session, participants must self-report no tobacco use within the last 24 hours and have a CO level < 6ppm. If they fail to abstain from tobacco products, they are rescheduled once. Our experience across many previous nicotine deprivation studies (33,58,86,126,127) with similar monetary incentives suggest fewer than 5% of participants will fail to abstain for their first scheduled deprivation session and require rescheduling. The majority of these participants will succeed in their second attempt. If they fail to abstain a second time, their participation is discontinued. These estimates are likely conservative given that the current sample is motivated to quit. As such, we do not expect attrition due to failure to abstain to bias the sample substantially. Following this, all participants complete a measure of their current affective state (PANAS), smoking urge (QSU) and withdrawal (WSWS) described earlier.

On completion of the task, participants receive brief cessation counseling, and combo NRT or placebo NRT according to their randomized treatment condition (see below).

C2.4 Treatment Groups

Participants are **randomly** assigned to one of two treatment groups: combination NRT (patch and lozenge) vs placebo NRT, both accompanying by motivational enhancement counseling. Due to the different visit calendars required for the two arms, study staff are not blinded to treatment arm.

Combination NRT: Participants assigned to the combo NRT arm will use 21-mg nicotine patches for 2 weeks. Participants will be given instructions on how to use the patch consistent with recommended use (20). They will be told to apply one patch each morning to a non-hairy body surface between the neck and waist. Moreover, they will be encouraged to report any side effects promptly so that steps may be taken to facilitate effective medication use (e.g., use of cortisone cream for skin reactions). Participants will also be provided with nicotine lozenges (2-mg). Participants will be instructed on recommended lozenge use (20). They will be encouraged to use at least one piece every 1-2 hours and to establish a consistent schedule to prevent rather than ameliorate craving and/or withdrawal symptoms. Both NRT patches and lozenges are over-the-counter “Up and Up” brand (purchased through Target.com).

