C2.5: Three week Ecological Momentary Assessment (EMA). Participants will provide three weeks of daily, real-time report of stressors, current affective state, urge to smoke, actual cigarette use, and medication use. These reports will be conducted 4x per day via Qualtrics surveys sent by text messages over cell phones. Loaner cell phones (iPhone 5s, with unlimited text, voice and data) are provided if the participant does not own a cell phone, must pay for text messages, or simply prefers not to use their own phone for the study. Participants will provide one week of baseline (pre-quit) reports and 2 weeks of post-quit date reports. The reports are designed to capture experiences in a distributed fashion throughout the day. The first report is programmed to occur at the participant's normal wake-up time. The second report will occur at a random time between wake-up and their midday, but at least one hour after their wake-up report. The third report will occur at a random time between their midday and one hour before bedtime, and the fourth report will occur at the participant's normal bedtime. If not available, participants can complete surveys for up to 60 minutes after prompt, after which the report is coded as missing. The reports are made via a brief (30 second) mobile-optimized Qualtrics survey. EMA research with similar parameters in our own and other laboratories (5,104,132,133) have met or exceeded guidelines that recommend > 80% response rate for valid assessment (134).

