At all 4 time points, participants report their **current affective state** (tense, anxious, or worried; irritable, frustrated, or easily angered; sad or depressed; happy, calm, or content) on a five point Likert scale (anchors: 0=Not at all, 4=Extremely). These affect items were selected from the Wisconsin Smoking Withdrawal Scale and have been demonstrated to load reliably on an affective distress factor associated with tobacco withdrawal (48,132). Participants also report if any **positive or negative stressful events** (separate questions) occurred since their last report (i.e., hassle or other stressful event; pleasant or positive event). If a positive or negative event occurred, they rate its intensity as well. If more than one event occurred in either category, they rate the most intense event in the category. Participants also report their current **urge to smoke** (on the Likert scale described above) and **how many cigarettes** (if any) they have smoked since their last report. Participants also report if they are wearing the patch (yes or no) and how many lozenges they have used since their last report.

These EMA methods follow directly from recent (and ongoing) published research on smokers' stress, affect, and cigarette usage in our Co-Is' ([name], [name]) laboratories at the Center for Tobacco Research and Intervention (5,8,104,132). In these studies, community smokers performed 4x per day reports for up to 10

weeks with high compliance rates, which demonstrates the clear feasibility of this method. CTRIs IVR infrastructure is available to us through our collaboration with Drs. [name] & [name].

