These EMA data are collected to evaluate the relationships between individual differences in psychophysiological affective response in our cued threat task (overall and deprived vs. non-deprived negative affect generally and fear/anxiety selectively) and real time, *in vivo*, affective response, smoking urge, and cigarette use. We will test if our laboratory-assessed psychophysiological individual differences predict individual variability in affective response, urge, and cigarette use recorded via EMA. We will also examine stress-affect, stress urge, and stress-smoking coupling (i.e., temporal covariation over 2 weeks post-quit between stressor experience, strength of affective response, and cigarette urge and use). We will also examine if any of these relationships differ across (i.e., are moderated by) Treatment Groups (Combo NRT with counseling vs. placebo NRT with counseling).

C2.5.1: Design Considerations and Justification. The use of EMA methods with 4X daily reports allows for increased precision with respect to temporal ordering of stressors, affect, smoking urge, and cigarette use. The survey was kept brief to decrease assessment burden. Similar (and longer) length surveys have been completed with high compliance (> 80% response rates) in Drs. [name] and [name]'s research with community smokers. We acknowledge that these reports are subjective based on the participants' individual appraisal of stressor severity and their own affective response to these stressors. However, these individual differences are at the core of our predictions regarding increased negative affective response across stressors among smokers, particularly when nicotine deprived. We predict that our laboratory measures will identify the smokers who will show consistently strong negative affect generally and in response to aversive stressors, and that these smokers will have poorer smoking cessation outcomes.

C2.6: Post-Quit Laboratory Visit

We will measure treatment adherence, additional treatment/medication usage, stressors, affective status, withdrawal, urge, and cigarette use for smokers at a follow-up laboratory visit at 2 weeks post-quit. This visit will also allow for biological confirmation of smoking status via CO measurement (CO < 6ppm).

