affect, cigarette use, and withdrawal symptoms. The within-subjects, repeated measures design associated with EMA survey make it suitable for **growth-curve modeling**, a technique that estimates change over time via **multilevel modeling** (147,148). Although time is not a focal factor in our analysis, growth curve modeling is well-suited for these data and our questions because it can easily accommodate missing data and unequal intervals between assessments that result from pseudo-randomly selecting assessment times during each day. This multilevel model allows us to predict “occasion-level” (level 1) responding associated with affective response, urge, or smoking with other occasion-level variables (e.g., stressor occurrence), or “person-level” (level 2) variables (e.g., startle potentiation measures from cued threat task). Therefore, these models will provide clear and powerful tests to determine if laboratory startle potentiation “biomarkers” of stress neuroadaptations predict individual differences in overall levels of negative affect, urge, or smoking over the 3-weeks of EMA controlling for stressor exposure (AIM 2.1). Furthermore, these same models will provide tests if startle potentiation measures of stress neuroadaptation predicts individual differences in the size of the occasion-level stressor effects on negative affect, urge and smoking (i.e., stress-induced negative affect, urge, and smoking). In other words, do our laboratory stress neuroadaptation measures predict stressor-affect, stressor-urge, and stressor-smoking covariation or coupling over time (AIM 2.2). Treatment condition can be included as a moderating between-subject factor to test if the relationship between startle potentiation and overall levels and coupling of EMA measured affect, urge and smoking differ generally when withdrawal symptoms are treated via combo NRT (AIM 4.3). As with GLM analyses, these multilevel models can accommodate other exploratory person-level moderators of these effects (e.g., trait anxiety, depression, level of dependence, sex). As before, the models can also include task as a factor to determine if anxiety as measured in the laboratory task displays comparable relationships with occasion-level EMA data

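### The EMA coupling models name no report-slot term, although stressor reports are likely to be rarer at wake-up. Average stressor coupling may be biased, and so may the arm and startle contrasts if the wake-up pattern or stressor timing differs by arm or startle.

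*Combined protocol and SAP*

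**What the plan says.** All references are to the combined protocol and SAP.

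- **Schedule (C2.5).** "These reports will be conducted 4x per day via Qualtrics surveys sent by text messages over cell phones". "The first report is programmed to occur at the participant's normal wake-up time", the second and third fall at random times before and after midday, and "the fourth report will occur at the participant's normal bedtime".
- **Items (C2.5).** Affect and urge are rated as they are at the moment of the report. Stressful and positive events are those that "occurred since their last report (i.e., hassle or other stressful event; pleasant or positive event").
- **Sample and treatment.** Entry requires that participants "smoke within the first 30 minutes of waking up" (C2.1). On the patch, "They will be told to apply one patch each morning to a non-hairy body surface between the neck and waist" (C2.4); lozenges are encouraged every one to two hours.
- **Questions.** C2.5 sets out stressor-affect and stressor-urge coupling over the two post-quit weeks and adds: "We will also examine if any of these relationships differ across (i.e., are moderated by) Treatment Groups". Aim 2.2 asks whether startle potentiation predicts coupling. Aim 4.3 asks whether combo NRT weakens the predictive strength of startle.
- **Model (Statistical Considerations, EMA analysis for Aims 2 and 4.3).** A multilevel model has stressor occurrence as the example occasion-level predictor, with startle and treatment at person level. On time it says: "Although time is not a focal factor in our analysis, growth curve modeling is well-suited for these data and our questions". No report-slot or time-of-day term is named.

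**The concern.** The stressor question covers the interval since the previous report, while the outcomes are momentary. If the bedtime report was answered, the interval behind the wake-up report is the night, when few stressors can occur. Stressor occurrence is therefore likely to be tied to report slot by design. If urge or affect on waking also differs from later in the day, slot confounds the occasion-level relation, and the stressor coefficient absorbs part of the difference between waking and the rest of the day.

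The contrasts the trial cares about need one more condition: the wake-up difference, or the timing of stressors, must itself vary by arm or by startle. That is plausible. The patch goes on in the morning, so any relief from active NRT could vary over the day. Waking follows overnight abstinence, and the trial's thesis is that startle marks the response to deprivation. If wake-up urge were relatively higher under NRT, the stressor-urge slope would look smaller in that arm, and this could pass for NRT weakening stress-induced urge. If it rose with startle, the Aim 2.2 coefficient would be pushed negative, against the hypothesis.

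**Working it through.** **1. The plan's own figure.** The 150 per group carried over to the EMA coefficients starts from N = 142. With two-sided alpha 0.05 (assumed), 90% power and 3 df, the noncentrality is 14.17, and 14.17 / 0.10 = 141.7, so 142. It reproduces, and this point does not change it.

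**2. Share of wake-up reports.** 1 of 4: 14 of 56 post-quit, 21 of 84 over three weeks.

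**3. Bias per unit of wake-up shift.** Without a slot term, the stressor coefficient is shifted by k x (wake-up level minus other slots), where k = P(wake-up | stressor) - P(wake-up | no stressor). The stressor rates below are assumptions.

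| Stressor rate at wake-up / other slots | P(wake-up given stressor) | P(wake-up given none) | k |
|---|---|---|---|
| 5% / 25% | 0.0125/0.2000 = 0.063 | 0.2375/0.8000 = 0.297 | -0.234 |
| 10% / 25% | 0.0250/0.2125 = 0.118 | 0.2250/0.7875 = 0.286 | -0.168 |
| 15% / 25% | 0.0375/0.2250 = 0.167 | 0.2125/0.7750 = 0.274 | -0.108 |
| 5% / 30% | 0.0125/0.2375 = 0.053 | 0.2375/0.7625 = 0.311 | -0.259 |

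Equal rates give k = 0. With k = -0.259 and a shared shift of 0.5 points, true coupling of 0.40 is estimated as 0.40 - 0.13 = 0.27. With k = -0.168 it is 0.40 - 0.08 = 0.32. The bias in a contrast is k times the *difference* in shift: for example -0.259 x 0.3 = -0.08.

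**4. Simulation.** Settings: 150 per arm, 56 reports, true coupling 0.40, no true difference by arm or startle. Assumed: stressors at 5% of wake-up and 30% of other reports, shared wake-up shift 0.5, slope SD 0.3, residual SD 0.9. Analysis: person-centred regression with cluster-robust errors, slot coded as wake-up or other, 300 runs, two-sided 5% (Monte Carlo error near 5% is about 1.3 points).

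| Pattern | Slot terms | Coupling, placebo arm | Arm difference (rejected) | Startle difference per SD (rejected) |
|---|---|---|---|---|
| Shared shift only | none | 0.27 | 0.00 (5%) | 0.00 (6%) |
| Shared shift only | slot | 0.40 | 0.00 (5%) | 0.00 (5%) |
| Plus 0.3 by arm, 0.15 per SD startle | none | 0.27 | -0.08 (39%) | -0.04 (39%) |
| same | slot only | 0.44 | -0.08 (34%) | -0.04 (39%) |
| same | slot, x arm, x startle | 0.40 | 0.00 (7%) | 0.00 (6%) |
| Plus 0.5 by arm, 0.25 per SD startle | none | 0.27 | -0.13 (78%) | -0.07 (74%) |
| same | slot only | 0.47 | -0.13 (81%) | -0.07 (77%) |
| same | slot, x arm, x startle | 0.40 | 0.00 (5%) | 0.00 (5%) |
| Shared shift, daytime stressors 30% vs 20% by arm | none | 0.27 | 0.03 (9%) | 0.01 (8%) |
| same | slot | 0.40 | 0.00 (4%) | 0.00 (4%) |
| 0.5 by arm, 0.25 per SD startle, but stressors 25% in every slot | none | 0.40 | 0.00 (8%) | 0.00 (6%) |

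**5. Other stressor rates.** With 25% in other slots, 5% to 15% at wake-up, 80% response and slope SD 0.2, the arm test rejects 9% to 29% for a 0.25-point arm difference and 22% to 72% for 0.5 points; with slot-by-arm terms it rejects 3% to 6%. At a 10% wake-up rate the figures are about 16% and 42%.

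**6. Aim 4.3.** For coupling this is startle x stressor x arm. At 10% / 25% and 80% response, slot-by-arm (0.5) and slot-by-startle (0.2) patterns leave that test at 5.5% with no slot term. If the wake-up pattern itself has an arm-by-startle component (0.2), it rejects 14% without slot and 11% to 14% with the two-way slot terms. Adding slot x treatment x startle brings it to 6%.

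**The case against.** The other side has real force on five counts.

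- A reader might infer that any time-of-day cycle will show up as an arm or startle difference. It does not: the shared-shift rows show both contrasts at zero. Smoking soon after waking is an entry criterion for both arms, so it supports a shared pattern.
- A reader might also infer that nicotine intake in the NRT arm is lowest at wake-up and that the placebo arm has no such cycle. The documents state neither. They do not say when a patch comes off, the survey stays open for 60 minutes after the prompt, and placebo participants who lapse would have an overnight gap of their own. Even the sign of an arm difference in wake-up urge is unknown.
- The wake-up window is not always the night. At 80% response, about one in five reaches back into the evening because the bedtime report was missed.
- Any distortion of Aim 2.2 from stronger morning urge in high-startle smokers would work against the hypothesis, not manufacture support for it.
- The section calls itself a set of exemplars and defers to a cited diary study, whose models may contain time terms. Calling time non-focal is not the same as leaving it out.

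All five stand as limits on the claim. None secures a slot term: the covariates of the cited study are not given, and a trend over days would not absorb a cycle within the day.

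**Conclusion.** The point holds in a conditional form. The design probably ties stressor occurrence to report slot, and the described model has nothing to separate the two. Average coupling is biased if wake-up urge or affect differs from later slots. The stressor x arm contrast (C2.5) and the stressor x startle contrast (Aim 2.2) may be biased as well, but only if the wake-up difference or the timing of stressors varies by arm or startle.

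The sizes above rest wholly on assumed stressor rates and urge shifts by slot. With equal stressor rates across slots the bias is zero. With a shared wake-up pattern and the same stressor timing in all groups, it is zero for the contrasts. The documents do not support a statement that the planned contrasts are wrong, or that Aim 4.3 is biased by two-way patterns alone. They do support stating the model more fully, because the protection costs almost nothing and uses data already planned.

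**What to change.** In the EMA models for current affect and urge:

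- Add report slot (wake-up, second, third, bedtime) as an occasion-level factor.
- Add slot x treatment for the treatment-moderation test in C2.5, and slot x startle for Aim 2.2. A slot main effect alone does not remove a differential bias.
- For Aim 4.3, also add slot x treatment x startle.
- Repeat the analyses without wake-up reports as a sensitivity analysis.

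The cost is SAP wording and a few model terms. Slot is known from the prompt schedule, so no new data, visits or participants are needed. In simulation the standard error of the startle-by-stressor coefficient was 0.022 to 0.023 with and without the slot terms, so there is no material loss of precision.

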All participants report some demographic information, their current affective state (Positive and Negative Affect Scales-PANAS (120), provide information on a broad-band personality measure (Brief Multidimensional Personality Questionnaire- bMPQ); (121) and supplemental measures of trait affectivity relevant to individual differences in anxiety including the Intolerance of Uncertainty Inventory, (122), and the Anxiety Sensitivity Inventory (123). Individual differences in depressive symptoms will also be recorded Center for Epidemiologic Studies Depression Scale Revised (CESD-R; 125) and the Depression Anxiety Stress Scale-21 (DASS-21).

These measures are available to serve as covariates to increase power to test for focal effects on relevant outcome measures. They are also available as possible individual difference moderators in supplemental analyses. After completing the self-report measures, participants schedule their first experimental session. Participants are randomized to either a nicotine deprived or non-deprived condition and instructed to abstain from all nicotine containing products for 24 hours prior to their nicotine deprived session or to continue their normal pattern of smoking prior to their non-deprived session.

Finally, participants receive brief cessation counselling, schedule their experimental visits and quit date, and are provided with verbal and written instructions about the 3-week daily EMA survey that begins one week before their quit date.

C2.3: Laboratory Experimental Session(s)

All participants complete the cued threat task (NPU; see section C3 below) in each of two separate experimental sessions. Their first session is either nicotine deprived and non-deprived in a counterbalanced order, the final is 2 weeks post-quit. The deprived group completes their first experimental session the day after the start of their quit attempt, and the non-deprived group completes it before the start of their quit attempt. Data across the two experimental sessions will be used to provide sensitive within-subjects tests of deprivation effects on startle potentiation measures of stress neuroadaptation (Aim 1) and to address all subsequent Aims (2-4).

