A. Adverse response to study medications. Participants will be made aware of the common side effects of the nicotine patch and lozenge that they are assigned to receive before they consent to participate in the study. It should be noted that the nicotine patch and lozenge are available over the counter, suggesting minimal risk. The nicotine patch has very few side effects, but up to 50% of participants may have a local skin reaction. Participants are instructed to stop using the patch or lozenge and inform us immediately if they experience nausea, dizziness, weakness, vomiting, fast or irregular heartbeat, mouth problems with the lozenge, or redness or swelling of the skin around the patch that does not go away. Participants are instructed to contact us if they experience any notable side effects from NRT. Participants are queried in person about side effect symptoms during their 1 and 2 week post-quit visits to the laboratory. [name] (a licensed psychologist and expert on the treatment of tobacco use disorder) is available if any psychiatric concerns emerge among study participants or if they have questions about the use of NRT.

B. Tobacco withdrawal. Tobacco withdrawal is associated with a number of unpleasant symptoms, such as sleep disturbance, hunger, craving, and negative mood. Though unpleasant, tobacco withdrawal symptoms pose no acute health risk. Most smokers have tried to quit in the past and are familiar with these phenomena. All smokers will be forewarned about these symptoms. Of course, smokers who are successful at quitting smoking cigarettes during the study will ultimately have reduced risk of a number of smoking-related health problems.

C. Adverse reaction to physiological sensor gel or application process. The sensor gel used is similar in salt concentration to human perspiration, reducing the possibility of this risk. In addition, research assistants will attend multiple training sessions including direct practice with sensor application prior to being cleared by the principal investigator to attach sensors to research participants.

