The Principal Investigator will be responsible for routine monitoring of the study's progress. This includes scheduled monthly meetings with study staff and review of written documentation. Data that are reviewed at these meetings include the number and type of participants enrolled, the number and reasons for exclusions from enrollment, the number treated and the stage of treatment, summary of adverse events, individual review of serious adverse events and study participation and outcome data. In addition, any unanticipated health events that raise concerns (e.g., serious mood or behavioral changes, suicidal ideation) will be immediately reported to the PI and the study physician.

To facilitate participant safety, study participants must meet study inclusion criteria. Once enrolled, study protocol will assess for the presence of adverse events at Week 2 post quit by querying participants as to whether they have experienced any adverse side effects associated with study medications. Participants will be queried about changes to health status, or experience with adverse events, at every study visit. Participants who report development of severe side effects associated with combo NRT (which is unlikely) will be instructed to discontinue study medication immediately and they will not be given more study medication. Such events will be immediately reported to the PI and study physician. If significant psychiatric or medical symptoms are reported verbally by participants during the regular questioning by study staff or study counsellors, the participant will be referred by the study staff, PI, and/or study physician, as needed, to the appropriate emergency medical or psychiatric services. Said services include the participant's primary care doctor, local therapy centers, urgent care clinics, UW walk-in clinics, or 911, depending on nature & severity.

B. Plans for assuring compliance with requirements regarding the reporting of adverse events.

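### The 1-week side-effect check claimed as a protection has no visit in the schedule, which leaves about 13 days of a 14-day course without a scheduled side-effect query

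*Combined protocol and SAP*

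**What the plan says.** Under Identification of and Protection against Risk, item A, the protocol says: "Participants are queried in person about side effect symptoms during their 1 and 2 week post-quit visits to the laboratory". The Data Safety and Monitoring Plan, section A, says instead that the "study protocol will assess for the presence of adverse events at Week 2 post quit", and adds that participants are asked about health changes or adverse events at every study visit. Participants who report severe side effects of combination NRT "will be instructed to discontinue study medication immediately and they will not be given more study medication".

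The visits are set out elsewhere. C1 states: "Participants return to the laboratory at 2 weeks post-quit". C2.3 gives two experimental sessions: "Their first session is either nicotine deprived and non-deprived in a counterbalanced order, the final is 2 weeks post-quit". It adds: "The deprived group completes their first experimental session the day after the start of their quit attempt"; the non-deprived group has its first session before the quit attempt. C2.4 places in-person counselling at screening, at 24 hours into the quit attempt and at 2 weeks. C2.6 and C3 describe the post-quit laboratory assessment as taking place at 2 weeks.

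On medication, C2.3 says: "On completion of the task, participants receive brief cessation counseling, and combo NRT or placebo NRT according to their randomized treatment condition". C2.4 gives a 2-week patch course. The ecological momentary assessment (EMA) survey in C2.5 covers adherence: "Participants also report if they are wearing the patch (yes or no) and how many lozenges they have used since their last report". No side-effect item is described.

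Three other places assume a one-week assessment: Aim 4.1, the design justification in C2.4.1, and the analysis of treatment outcome under Statistical Considerations.

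**The concern.** A safeguard listed in the participant-protection section should correspond to a visit that takes place. Here the two safety sections disagree on when side effects are asked about, and the schedule supports only the later time. Staff working from the schedule would have no occasion to make the 1-week query, while a reader of the risk section would believe that it is made.

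Without that query, learning of a problem during the course depends on participants volunteering it. The scheduled data become a recall at the end of the course from those who attend the 2-week visit. C2.4 wants side effects reported promptly so that staff can help participants keep using the medication; a query at the end of the course cannot serve that purpose.

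**Working it through.** The plan gives no figure to reproduce. The check is a calendar with quit day as day 0.

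**Inputs from the protocol**
- Screening and first counselling: about day −7 (C2.4).
- First experimental session: before day 0 for the non-deprived group, day 1 for the deprived group (C2.3).
- Second counselling contact: 24 hours into the quit attempt, about day 1 (C2.4).
- Dispensing: on completion of the task at the experimental session (C2.3).
- Course: 2 weeks, one patch each morning (C2.4).
- Final visit: 2 weeks post-quit (C1, C2.3, C2.6).

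**Assumptions.** There are 14 patches, one a day. The first is used on day 0 if dispensed before the quit day, or on day 1 if dispensed at the day-1 session. The final visit is on day 14. The protocol does not state the day of first use for the non-deprived group.

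**What the contact at about 24 hours covers.** The deprived group must have abstained from all nicotine products for 24 hours before its session (C2.2) and receives medication after the task. A query at that contact is therefore at or before dispensing and is not an on-drug query. In the non-deprived group it covers about one day of use at most.

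**Interval without a scheduled query.** 14 − 1 = 13 days.

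**Treatment left at each query** (the patch for the day of the visit is counted as remaining)

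| First patch | Days covered | Left at day 7, if that visit existed | Left at day 14 |
|---|---|---|---|
| Day 0 | 0–13 | 14 − 7 = 7 | 14 − 14 = 0 |
| Day 1 | 1–14 | 14 − 6 = 8 | 14 − 13 = 1 |

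A real 1-week visit would fall with 7 to 8 of 14 patch-days still to come. The 2-week visit falls with 0 to 1.

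**Channel already in use.** Four surveys a day over 14 post-quit days is 4 × 14 = 56 prompts. They ask about patch wear and lozenge count, and no side-effect question is described.

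**Scale of expected effects.** The risk section says that up to 50% of participants may have a local skin reaction to the nicotine patch. With 150 in the active arm, that is at most 0.50 × 150 = 75. This is an upper bound on local reactions and does not count severe ones.

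**The case against.** A reader might infer that the side-effect query comes too late for the stopping rule to act. The documents do not support that. The risk section tells participants to stop the product and inform the study at once for listed symptoms, and to make contact about any notable side effect. C2.4 encourages prompt reporting. The discontinuation provision in the monitoring plan is triggered by a participant's report and is not tied to a visit. All of these can operate on any day. C2.6 and C3.3 also treat the 2-week assessment as taking place during medication use, so it would be wrong to call it off-drug.

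It can also be said that the monitoring plan requires a query at every study visit and mentions regular questioning by staff and counsellors. That is right, and the plan is not limited to Week 2. But no visit is scheduled between about day 1 and 2 weeks at which this rule could apply.

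If a 1-week visit does in fact occur, as Aim 4.1, C2.4.1 and the outcome analysis imply, most of the gap closes. The contradiction remains, because the schedule omits the visit.

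A second tempting inference is that those with the worst reactions fail to return, so that tolerability by arm is understated. The documents give no return rates and nothing linking reactions to non-return, and a comparison of tolerability between arms is not among the aims or planned analyses. The point does not rest on it.

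On the remedy, C2.5.1 says the survey was kept brief on purpose, and repeated symptom questions could cue participants to their arm where C2.4 relies on a believable placebo. This stands as a reason to prefer one neutral question to a symptom checklist with automatic alerts.

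**Conclusion.** The concern holds as an internal contradiction with a practical consequence. The risk section, Aim 4.1, C2.4.1 and the treatment-outcome analysis assume a one-week assessment; C1, C2.3, the counselling schedule in C2.4, C2.6 and C3 have none; and the monitoring plan names only Week 2 for the medication query. As scheduled, about 13 days pass without a side-effect query, and 0 to 1 treatment days remain at the 2-week query, compared with 7 to 8 at the 1-week visit that is claimed. A staff-directed stop prompted by the 2-week query would have almost no treatment left to act on.

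The loss is confined to the scheduled mid-course check. Stopping on a participant's own report is unaffected. The figures rest on one patch a day for 14 days, first use on day 0 or day 1, and a final visit on day 14. That the survey has no side-effect item rests on its description in C2.5.

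**What to change.** Reconcile the risk section (item A), Aim 4.1, C2.4.1, the treatment-outcome analysis and section A of the monitoring plan with the visit schedule. State once which visits exist and at which of them side effects are asked about. If a 1-week visit takes place, enter it in C1 and the sections that follow.

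If it does not, remove the claim and replace the lost check:
- Add one brief, neutrally worded yes/no side-effect question to an existing post-quit EMA survey, for example the bedtime one, identical in both arms.
- Have staff review positive answers under the pathway already in section A of the monitoring plan.
- Ask the same question by text or phone of anyone who misses the 2-week visit.

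The cost is protocol wording, one item in an existing Qualtrics survey, a few seconds of burden for participants and some follow-up calls. There is a small risk of cueing participants to their arm, which neutral wording limits. No change to any dose or stopping criterion is proposed.
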